7.3. Deaths and Serious Adverse Events

Deaths and other serious adverse events will be listed if any of these events occur. Adverse Events Leading to Discontinuation of Investigational Product and/or Withdrawal from the Study and Other Significant Adverse Events

A by-subject listing of AEs leading to withdrawal will be provided.

Patient profile for deep venous thrombosis/pulmonary embolus will be generated for cardiovascular event.

7.4. Pregnancies (as applicable)

If any female subjects become pregnant during the study, a narrative of such subjects will be provided.

7.5. Clinical Laboratory Evaluations

A listing of reference ranges for clinical laboratory tests performed during the study will be generated. Hematology, clinical chemistry and urinalysis (listing only) data will be listed by subject, phase, visit, and actual date and time and summarized by treatment and visit. Summary of change from baseline in hematology and clinical chemistry by treatment and visit will be created for each site. If any laboratory test results are outside of the reference range, they will be flagged with high/low and/or toxicity grade in the listing. Only the tests which have specified in the protocol will be included on the displays.

Laboratory abnormalities that are recorded as adverse events will be listed separately and corresponding lab values will be provided.

Modified Division of AIDS (DAIDS) AE grades will be derived in analysis dataset by using Division Of AIDS Table For Grading The Severity Of Adult And Pediatric Adverse Events Version 2.0, November 2014. Grades 2, 3, and 4 of lab abnormalities will be listed by Site, subject, phase, visit, treatment and actual date and time.

7.6. Other Safety Measures

Vital sign data (temperature, systolic and diastolic blood pressure, and pulse rate) will be summarized by treatment, visit, and planned time and listed by site, subject, phase, visit, planned time, and actual date and time. In addition, a listing of vital signs for subjects with abnormalities of potential clinical importance will be provided.

ECG data will be listed by site, subject, visit, and actual date and time. Clinically significant ECG abnormalities will be flagged.

Any surgical procedures will be listed.

Medical and medication history, physical examination, pregnancy and drug screen (including alcohol) results will be captured in the source document supporting the enrolment criteria and summary will not be provided.

MRI images and quantitative assessments will be collected and reported separately by GSK Platforms Technology Sciences. Only MRI collection dates will be provided in the listing package.

8. PHARMACOKINETIC ANALYSES

The reconciliation of the PK Case Report Form (CRF) and SMS2000 data will be performed by, or under the direct auspices of, Clinical Pharmacology Sciences and Study Operations (CPSSO), GlaxoSmithKline.

The merge of PK concentration data, randomisation and CRF data will be performed by, or under the direct auspices of, Clinical Statistics (Programmer), GlaxoSmithKline.

Derivation of pharmacokinetic parameters will be performed by, or under the direct auspices of, Clinical Pharmacokinetic Modelling Simulation (CPMS), GlaxoSmithKline.

Statistical analysis of pharmacokinetic parameters will be performed by, or under the direct auspices of, Clinical Statistics (Statistician), GlaxoSmithKline.

	Pharmacokinetic Concentration Data					
PC Windows Non- Linear (WNL) File	PC WNL file (CSV format) for the non compartmental analysis by Clinical Pharmacology Modelling and Simulation function will be created according to GSK PK guidance Note: Concentration values will be imputed as per GUI_51487					
Descriptive Summary Statistics, Graphical Displays and Listings	Refer to IDSL PK Display Standards. Refer to IDSL Statistical Principle 6.06.1. Note: Concentration values will be imputed as per GUI_51487 for descriptive summary statistics/analysis and summarized graphical displays only.					
Pharmacokinetic Para	ameter Derivation					
PK Parameter to be Derived by Programmer	The following PK parameters will be derived or extracted from SDTM PC file or SDTM PP by the Programmer: From SDTM PC Concentrations: Ctau on Day 29, C48h, C8d, CWk4, CWk8, CWk12, CWk24, CWk36, and CWk52 from concentration data (as data permit) & the ratios: VT:blood plasma, CT:blood plasma, CVF:blood plasma, CT:CVF, VT:CVF in women, and RT:blood plasma, RF:blood plasma and RT:RF in men and women (as data permit) at matched timepoints evaluated. From SDTM PP file: VT:blood plasma, CT:blood plasma, CVF:blood plasma, CT:CVF, VT:CVF in women, and RT:blood plasma, RF:blood plasma and RT:RF in men and women ratios for Cmax, AUC(0- ∞), AUC(0-last), AUC(0-Wk4), AUC(0-Wk8) and AUC(0-Wk12)					
Pharmacokinetic Para	ameter Data					
Is NQ impacted PK Parameters Rule Being Followed	Yes, refer to Standards for the Transfer and Reporting of PK Data using HARP.					
Descriptive Summary Statistics, Graphical Displays and Listings	Refer to IDSL PK Display Standards & refer to Standards for the Transfer and Reporting of PK Data using HARP.					

8.1. Reporting Standards for Pharmacokinetic

8.2. Drug Concentration Measures

CAB concentrations will be collected at following time points after a single CAB 600 mg IM dose:

- Blood plasma (BP) of CAB concentrations: Day 1 (pre-dose, 4hr), Day 3 (C48h), Day 5 (C96h), Day 8 (C168h), Weeks 4, 8, 12, 24, 36, and 52 (CWk4, CWk8, CWk12, CWk24, CWk36 and CWk52)
- Cervical tissue (CV) and cervicovaginal fluid (CVF) of CAB concentrations in women: Day 3 (C48h), Day 8 (Cd8), Weeks 4, 8, and 12 (CWk4, CWk8, and CWk12)
- Rectal tissue (RT) and rectal fluid (RF) in men and women (as data permit): Day 3 (C48h), Day 8 (Cd8), Weeks 4, 8, and 12 (CWk4, CWk8, and CWk12)

• Vaginal tissue (VT) of CAB concentrations in women: Day 3 (C48h), and Week 8 (CWk8)

These concentrations will be determined directly from concentration-time data from each matrix (BP, CV, CVF, RT, RF, VT). Descriptive statistics (i.e. mean, standard deviation, median, minimum and maximum) and graphics will be created to describe the primary PK endpoints of interest.

Refer to the standard operating procedure, SOP-CPK-0001, for more information regarding the treatment of plasma concentrations below the assay's lower limit of quantification (BQL).

Individual concentration-time profiles and median/mean profiles from each matrix will be plotted. Each of the figures will contain one plot on the untransformed scale (i.e. a linear plot) and one plot on the log transformed scale (i.e. semi-log plot). See Section 11.1.3 Pharmacokinetic Figures and Tables for details.

8.3. Deriving and Summarizing Pharmacokinetic Parameters

Pharmacokinetic analyses will be the responsibility of the Clinical Pharmacokinetics Modeling & Simulation department within GlaxoSmithKline.

Plasma and tissue/fluid concentration-time data will be analyzed by non-compartmental methods with Phoenix WinNonlin 7 or higher (New Jersey). Pharmacokinetic parameters will be estimated via noncompartmental analysis using the linear up/log down application of the trapezoidal rule for model 200 (extravascular administration) of the WinNonlin program. Calculations will be based on the actual sampling times recorded during the study. The following CAB PK parameters will be calculated for each matrix if available:

- Cmax, tmax, AUC(0-∞), AUC(0-last), AUC(0-Wk4), AUC(0-Wk8) and AUC(0-Wk12) and t¹/₂ in blood plasma and in CT, and CVF in females and RT and RF in males and females.
- CAB concentrations at Day 3 (C48h), Day 8 (Cd8), Weeks 4, 8, and 12 (CWk4, CWk8, and CWk12) in blood plasma and in CT, CVF in women, and in RT and RF in men and women (as data permit) will be considered as evaluable data if they are collected within 4 hours of schedule time for C48h and Cd8, and collected within ± 3 days of scheduled time for CWk4, CWk8 and CWk12. Actual weeks (rounding to the integer weeks) will be used for CWk24, CWk36 and CWk52.
- 2. VT samples will be considered as evaluable C48h and CWk8 concentration if samples are collected at Day 3 (C48h with 4hrs of window of scheduled collection), and Week 8 (CWk8 with ± 3 days of scheduled visit), in women following a single CAB 600 mg IM dose.
- 3. CAB concentration in VT, CT, CVF, RT, RF and BP on Day 29 will be considered as evaluable data if these samples are collected within 4hr of scheduled window.

- 4. The area under the plasma concentration-time curve from time zero to the last quantifiable concentration (AUC(0-last)) will be determined using the linear trapezoidal rule for increasing concentrations and the logarithmic trapezoidal rule for decreasing concentrations in blood plasma and in CT, and CVF in females and RT and RF in males and females.
- 5. The AUC extrapolated to infinity $(AUC(0-\infty))$ will be calculated, where data permit, as the sum of AUC(0-t) and Ct/ λz , where Ct is the observed plasma concentration obtained from the log-linear regression analysis of the last quantifiable time-point in blood plasma and in CT, and CVF in females and RT and RF in males and females.
- 6. AUC(0-Wk4), AUC(0-Wk8) and AUC(0-Wk12) are the area under the concentration time curve from time zero to week 4, week 8 and week 12 respectively, determined using the linear trapezoidal rule for increasing concentrations and the logarithmic trapezoidal rule for decreasing concentrations in blood plasma and in CT, and CVF in females and RT and RF in males and females.
- 7. The first occurrence of the maximum observed plasma concentration (Cmax) will be determined directly from the raw concentration-time data in blood plasma and in CT, and CVF in females and RT and RF in males and females.
- 8. The time at which Cmax is observed (tmax), determined directly from the raw concentration-time data in blood plasma and in CT, and CVF in females and RT and RF in males and females.
- 9. The apparent terminal elimination half-life (t1/2) obtained as the ratio of $\ln 2/\lambda z$, where z is the terminal phase rate constant estimated by linear regression analysis of the log transformed concentration-time data in blood plasma and in CT, and CVF in females and RT and RF in males and females.
- 10. Ratios of time-matched AUC(0-∞), AUC(0-last), AUC(0-Wk4), AUC(0-Wk8) and AUC(0-Wk12) tissue matrices/luminal fluid: blood plasma (CVF:BP, CT:BP, RT:BP, and RF:BP), where data permit.
- 11. CVF:BP, CT:BP, VT:BP, CT:CVF, VT:CVF ratio in women and, RT:BP, and RT:RF ratios in males and females at matching time points (48h, 8d, 4w, 8w, 12w) where data permit during the injection phase, are calculated by CAB concentration in one of the matrices divided by another specified matrix. For example, the ratio of CVF, CT, VT, and RT concentration to blood plasma will be calculated as R_CVF (CT, VT, RT) = CVF (CT, VT, RT) concentration (ng/g) / Plasma Concentration (ng/mL). Assuming tissue density of 1g/mL, the tissue concentration to plasma ratio will be unitless. For CVF, CT, VT, and RT concentration below lower level of qualification (LLQ), it will be imputed as half of LLOQ.

Plasma PK parameters should be reported in μ g/mL and μ g•h/mLfor Cmax and AUC and in hours for tmax. Tissue concentrations in ng/g will be converted to ug/mL assuming a 1g/mL density and 1000ng/ug.

Clinical statistics and programming will extract the Ctau on Day 29, Day 3 (C48h), Day 8 (C8d), Weeks 4, 8, and 12 (CWk4, CWk8, and CWk12) from concentration data to calculate the ratios: CVF:BP, CT:BP, VT:BP, CT:CVF, VT:CVF ratio in women and, RT:BP, RF:BP and RT:RF ratios in males and females at matching time points where data permit during the injection phase.

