The CAB population PK model has been updated with PK data from ÉCLAIR (an additional 94 males) and LATTE-2 (an additional 230 participants; 216 males and 14 females), significantly increasing the data in the population PK dataset. The absorption rate constant for the entire population following CAB LA for the new model was increased approximately 2-fold ($4.54 \times 10^{-4} \text{ hr}^{-1}$ to $9.19 \times 10^{-4} \text{ hr}^{-1}$; i.e., more rapid absorption) as compared to the previous model and resulted in higher peak to trough ratios than previously observed. Sex remains a significant covariate in the model affecting the absorption rate constant following LA administration (KA LA), reflecting slower absorption in females than in males. Additional data from HPTN077 will increase the data obtained from females in the model to improve understanding of the impact of sex on KA LA.

Simulations based on the updated population PK model have been conducted to evaluate several potential dosing regimens. Currently, the HPTN077 Cohort 2 regimen (CAB LA 600 mg IM at two time points 4 weeks apart and every 8 weeks (Q8W) thereafter) is planned for evaluation in long-term Phase 3 PrEP studies. CAB LA 600 mg IM is the largest CAB LA dose that can be administered by single injection (3mL of 200 mg/mL nanosuspension). For these reasons, a single 600 mg IM is the proposed dose for evaluation of plasma and tissue PK in this study. Simulated profiles following a single CAB LA 600 mg IM injection one week after discontinuation of the CAB 30 mg once daily oral lead-in to evaluate safety are shown for males and females separately (Figure 2, Figure 3). The profiles show the last oral dose, which are expected to achieve mean peak and trough concentrations of 7.5 $\mu\text{g/mL}$ and 4.2 $\mu\text{g/mL}$, respectively. Consistent with the impact of sex on absorption, males will achieve a higher C_{max} of ~3 $\mu\text{g/mL}$ than females, who will achieve a C_{max} of ~1.35 $\mu\text{g/mL}$. Plasma concentrations are expected to remain above 4x PA-IC₉₀ (0.664 $\mu\text{g/mL}$) for approximately 4 weeks and above PA-IC₉₀ (0.166 $\mu\text{g/mL}$) for approximately 8 weeks in 95% of males; greater variability in concentrations between 8 and 12 weeks post injection is expected in males. Plasma concentrations are expected to remain above the PA-IC₉₀ (0.166 $\mu\text{g/mL}$) in 95% of females throughout the 12-week tissue sampling period.

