5.6.2.1. Evaluable Concentrations and Parameters

Flags for evaluable concentrations for each type of samples will be created and are defined as samples collected within the specified window without major protocol deviations. Evaluable parameters are calculated based on evaluable concentrations.

Flags will be created for the samples which are collected when the injections are done at gluteal muscle under ultrasound guidance. Concentrations data could be summarized by gluteal muscle flag.

For the purposes of calculating summary statistics and for statistical analysis, only parameters with the exception of tmax will be log_e transformed.

Between subject's coefficient of variation (%CVb) will be calculated according to the following methods:

Untransformed Data : 100 * (SD/Mean)

Transformed Data : $100 * (sqrt(exp(SD_{log}^2)-1))$

where SD_{log} indicates the standard deviation of log-transformed data.

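### SAP 5.6.2.1 and 8.3 let a Day 8 sample taken more than 4 h off schedule drop out of Cmax and AUC, or disqualify them, although both are calculated at actual times

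*SAP*

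**What the plan says.** Four statements in the SAP bear on this.

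- Section 8.3, item 1, sets the windows. Day 3 and Day 8 samples are evaluable if "collected within 4 hours of schedule time for C48h and Cd8"; later ones if "collected within ± 3 days of scheduled time for CWk4, CWk8 and CWk12".
- Section 5.6.2.1 carries the flag over to the parameters: "Evaluable parameters are calculated based on evaluable concentrations".
- The opening text of Section 8.3 says of the NCA: "Calculations will be based on the actual sampling times recorded during the study".
- Section 8.3, items 7 and 8, say that Cmax and tmax are "determined directly from the raw concentration-time data in blood plasma and in CT" and the other sampled matrices, with no mention of an evaluability filter.

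Under SAP 8.2, cervical tissue, cervicovaginal fluid, rectal tissue and rectal fluid are sampled after the injection at 48 h, Day 8 and Weeks 4, 8 and 12. Plasma has the same visits plus 4 h, Day 5 (96 h) and Weeks 24, 36 and 52. Vaginal tissue is taken only at 48 h and Week 8.

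In SAP Section 4, the population used for tissue and fluid parameter summaries, mean and median plots and ratios requires both evaluable plasma and evaluable tissue or fluid parameters.

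**The concern.** A collection window protects a nominal-time summary: a value labelled Day 8 should have been taken close to Day 8. It protects nothing in Cmax or AUC when each concentration enters the NCA at the time it was actually drawn. Carrying the flag into the parameters therefore has a cost and no matching gain.

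The SAP also does not say how the flag acts on a parameter. One reading deletes the sample and recalculates. Tissue and fluid have only five post-dose samples, and Day 8 is the one nearest the expected peak. The other reading marks the whole parameter non-evaluable, so the subject leaves the evaluable displays. The programmer would have to choose, and items 7 and 8 point to a third answer, in which Cmax and tmax ignore the flag. At stake are the tissue and fluid Cmax and AUC and their ratios to plasma, which are secondary endpoints.

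**Working it through.** The plan gives no figure on this point, so there is none to reproduce.

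**Inputs**

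- Absorption constant ka: 9.19×10⁻⁴/h from the updated population model in Protocol 4.5 ("The absorption rate constant for the entire population following CAB LA for the new model was increased approximately 2-fold"), used here for men. For women, 4.54×10⁻⁴/h, the previous model's whole-population value. This is an assumption: Protocol 4.5 says women absorb more slowly but gives no female value.
- Elimination constant ke: not stated. Inferred from the oral peak and trough in Protocol 4.5: ln(7.5/4.2)/24 = 0.0242/h, half-life 28.7 h.
- Tissue and fluid are assumed proportional to plasma.

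**Model.** C(t) ∝ exp(−ka·t) − exp(−ke·t), and tmax = ln(ke/ka)/(ke − ka). This gives tmax of 141 h (men) and 168 h (women). At 168 h the concentration is 99% and 100% of peak.

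**Size of the timing difference**

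| Shift | Men's ka | Women's ka |
|---|---|---|
| 4 h at 48 h | 3.9-4.4% | 4.1-4.5% |
| 4 h at Day 8 | 0.2% | 0.01% |
| 5 h at Day 8 | 0.2% | 0.01% |
| 3 days at Weeks 4-12 | 6.4-6.8% | 3.2-3.3% |

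**Removing Day 8 from tissue or fluid.** Relative concentrations at 48, 168 and 672 h are 0.643, 0.840 and 0.539 (men) and 0.665, 0.909 and 0.737 (women).

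- Cmax, men: 0.643/0.840 − 1 = −23%, and tmax moves to 48 h. Women: 0.737/0.909 − 1 = −19%, and tmax moves to Week 4.
- AUC(0-Wk4) by the linear-up/log-down rule, where a rising segment is Δt(C1+C2)/2 and a falling one is Δt(C1−C2)/ln(C1/C2). Men, with Day 8: 15.4 + 89.0 + 341.9 = 446.3; without: 15.4 + 368.0 = 383.4, a change of −14%. Women: 523.8 against 453.4, −13%.
- AUC(0-Wk12). Men: 862.5 against 799.6, −7%. Women: 1265.3 against 1194.9, −6%.

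**Removing Day 8 from plasma.** The Day 5 sample limits the loss. Cmax: 0.817/0.840 − 1 = −2.7% (men) and 0.859/0.909 − 1 = −5.5% (women). AUC(0-Wk4) changes by −3.6% and −3.4%, AUC(0-Wk12) by −1.9% and −1.4%, AUC(0-∞) by −1.6% and −0.8%.

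**Ratios.** If both Day 8 samples go, the losses do not cancel. The tissue:plasma Cmax ratio changes by (1−0.234)/(1−0.027) − 1 = −21% (men) and (1−0.189)/(1−0.055) − 1 = −14% (women).

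**Keeping the sample.** A tissue sample 5 h off schedule, entered at its actual time, changes Cmax by at most 0.23% and AUC by at most 0.05%.

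**Effect on a group mean.** With 1 of 8 subjects affected, the geometric mean tissue Cmax moves by (1−0.234)^(1/8) − 1 = −3.3%, and AUC(0-Wk4) by (1−0.141)^(1/8) − 1 = −1.9%.

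**Sensitivity.** With disposition half-life assumed at 20-60 h and long-acting half-life at 21-64 days, the loss in an affected subject is 6-39% for tissue Cmax, 8-25% for tissue AUC(0-Wk4) and 0-18% for plasma Cmax. The 4 h difference at Day 8 ranges from 0.01% to 0.65%.

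**The case against.** The best defence is that SAP 5.6.2.1 defines a flag and nowhere orders a sample deleted and the NCA rerun. Items 7 and 8 of Section 8.3 read Cmax and tmax from raw data, which would leave Cmax untouched. Section 5.6.2 has the team review samples with protocol deviations before excluding them from summary tables. Section 11.1.3 asks for each flag level plus overall where a display is specified by evaluable flag, as Table 3.6 is, and the listings carry the flags. No data vanish from the report.

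Much of this stands. A reader might infer that the plan biases the study's Cmax and AUC by 14-23%. The documents do not support that. The loss arises only if the sample is removed, only in a subject whose Day 8 sample is out of window, and at that size only in CT, CVF, RT and RF; the 14% applies to AUC(0-Wk4) alone. Plasma, the only matrix in the ANCOVA by sex, loses far less.

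The defence does not remove the conflict. Ratio Tables 3.8 to 3.11 are planned by site and gender with no flag split, in a population that requires evaluable parameters. Table 3.4, the comparison by sex, is limited to evaluable data. The flag-the-parameter reading avoids the downward shift but loses the subject.

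A reader might also conclude that the Cd8 window should be widened, since the profile is flat there. That does not follow. Protocol 7.5 holds first-week sampling to schedule, and a wider window could loosen the time matching of plasma and tissue.

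**Conclusion.** The point holds as a conflict between SAP 5.6.2.1 and 8.3 that should be resolved before programming. Under either reading of the flag, a Day 8 sample outside the window costs an affected subject something, over a timing difference of about 0.2% at 4-5 h in the base case. Removal lowers that subject's tissue and fluid parameters by the amounts shown, with a much smaller loss in plasma and none in vaginal tissue. Flagging costs a subject from about 8 per sex in the evaluable summaries and ratios.

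The percentages are illustrative. They depend on an inferred ke, a women's ka borrowed from an older whole-population model, and tissue kinetics proportional to plasma. The plasma figures also assume that Day 5 stays usable; the SAP gives no window for it. The documents do not indicate how many samples will be out of window, so no study-level bias can be stated. In the scenarios examined, removing the sample never raised Cmax or AUC; only the size of the loss is uncertain.

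**What to change.** In SAP 5.6.2.1 and 8.3, state that:

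1. the collection-window flag applies only to nominal-time concentration summaries (C48h, Cd8, CWk4, CWk8, CWk12 and so on) and to matched concentration ratios;
2. out-of-window samples stay in the NCA at their actual times for Cmax, tmax, all AUCs and t½;
3. timing alone does not make a parameter non-evaluable.

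Leave the 4 h Cd8 window and the protocol's instruction to sample on schedule in the first week unchanged. The cost is SAP wording and the matching programming specification. No visit, sample or protocol change is needed, and the nominal-time summaries keep their present protection.

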9.4.2. Secondary Analyses

Safety data will be presented in tabular and/or graphical format and summarized descriptively according to GSK's Integrated Data Standards Library (IDSL) standards.

Plasma and tissue/fluid concentration-time data will be analyzed by non-compartmental methods with WinNonlin 5.2 or higher (Pharsight, Inc., Cary, NC). Pharmacokinetic parameters will be estimated via noncompartmental analysis using the linear up/log down application of the trapezoidal rule for model 200 (extravascular administration) of the

WinNonlin program. Calculations will be based on the actual sampling times recorded during the study. The following PK parameters will be calculated if available:

 • CVF:BP, CT:BP, VT:BP, CT:CVF, VT:CVF ratio in women and, RT:BP, and RT:RF ratios in males and females at matching time points where data permit during the injection phase.

 • C_{max}, t_{max}, AUC(0-∞), AUC(0-last), AUC(0-Wk4), AUC(0-Wk8) and AUC(0-Wk12) and t_{1/2} in blood plasma and in CT, and CVF in females and RT and RF in males and females. • Ratios of time-matched AUCs tissue matrices/luminal fluid: blood plasma where data permit.

 • CAB concentration in VT, CT, CVF, RT, RF and BP on Day 29 of the oral lead-in phase prior to IM injection

Ratios will be calculated for each subject. Evaluable PK parameters and calculated ratios will be summarized by gender and/or overall for each matrix. A sex-based comparison will be made for all the evaluable blood plasma PK parameters and estimated ratio between females vs males and its associated 90% CI will be provided. Covariates of BMI and other factors may also be considered in the model for the blood plasma PK parameter comparison. CAB concentration in each matrix from the oral lead-in phase may be compared with Weeks 4, 8, and 12 concentrations if data permit. The relationship between the plasma CAB PK concentration with time matched CVF, CT, VT, RT and/or RF will be assessed with plots and by the SAS Proc Corr procedure.

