3.4	Evaluable PK Plasma Parameter Summary	GSK1265744/LAI114433, Table 11.7	Summary of Result of Plasma Cabotegravir PK Parameter Comparisons Between Gender for Evaluable PK	Limited to evaluable PK data, and include sex and BMI in model, evaluate the difference between gender for AUC(0-t), AUC(0-∞), Cmax, AUC(0- Wk4), AUC(0-Wk8), AUC(0-Wk12) and t1/2,	3	SAC
3.5	Evaluable PK Plasma Parameter Summary	GSK1265744/LAI114433, Table 11.7	Summary of Result of Plasma Cabotegravir PK Parameter Ctau Comparisons Between Oral and IM for Evaluable PK	Limited to evaluable PK data, and include sex, BMI and Visits in model, evaluate the difference between IM vs oral CAB Ctau	3	SAC
3.6	Evaluable Tissue_fluid and PK Parameter(IM)	GSK1265744/LAI114433 Table 11.10	Summary of Tissue and Fluid Cabotegravir Parameters for each Treatment and Matrix by Site, by Evaluable Flag and by Gender	Include the CAB Parameters from tissue/fluid on Day 29 of oral lead-in, put each by variable on different page or sub-category	2	SAC
3.7	Tissue fluid Parameter	GSK1265744/LAI114433 Table 11.8	Listing of Derived Tissue and Fluid Cabotegravir Parameters	Sort by clinical site, sex and subject ID and flags for evaluable and injection locations	1	SAC

Table No.	Population	IDSL No. / Example Shell	Title	Programming Notes	QC Level	Deliverable Priority
3.8	Evaluable Tissue_fluid and PK Parameter (IM)	GSK1265744/LAI114433 Table 11.10	Summary of Tissue and Fluid to Blood Plasma Cabotegravir PK Parameter Ratio for each Matrix by Site and by Gender	Ratios of Tissue or fluid vs plasma for AUC(0-t), AUC(0-∞), Cmax, AUC(0- Wk4), AUC(0-Wk8), AUC(0-Wk12), for VT:blood plasma, CT:blood plasma, CVF:blood plasma, by site, by gender and overall	2	SAC
3.9	Evaluable Tissue_fluid and PK Parameter (IM)	GSK1265744/LAI114433 Table 11.10	Summary of Tissue and Fluid to Blood Plasma Cabotegravir PK Concentration Ratios of Each Visit by Site and by Gender	Ratios of Tissue fluid vs plasma for oral C29d, and IM C3d, C8d, CWk4, CWk8, CWk12 of VT:blood plasma, CT:blood plasma, CVF:blood plasma, by site, by gender and overall	2	SAC
3.10	Evaluable Tissue_fluid and PK Parameter(IM)	GSK1265744/LAI114433 Table 11.10	Summary of Tissue to Fluid Cabotegravir Parameter Ratios by Site and by Gender	Ratios of tissue vs fluid for AUC(0-t), AUC(0-∞), Cmax, AUC(0-Wk4), AUC(0- Wk8), AUC(0-Wk12), by site and by gender plus overall for ratios: CT:CVF, VT:CVF in women, and RT:RF in men and women (as data permit)	2	SAC

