3.11	Evaluable Tissue_fluid and PK Parameter Population (IM)	GSK1265744/LAI114433 Table 11.10	Summary of Tissue to Fluid Cabotegravir PK Concentration Ratios of Each Visit by Site, by Gender	Ratios of Tissue vs fluid for oral C29d, and IM C3d, C8d, CWk4, CWk8, CWk12 of for ratios: CT:CVF, VT:CVF in women, and RT:RF in men and women (as data permit)	2	SAC
3.12	Tissue fluid Parameter	GSK1265744/LAI114433 Table 11.8	Listing of Individual Tissue and Fluid to Blood Plasma or Tissue vs Fluid Cabotegravir PK Concentration Ratios	Ratios of tissue fluid vs plasma or tissue vs fluid for oral C29d, and IM C3d, C8d, CWk4, CWk8, CWk12, include flags for evaluable data and injection location variables	2	SAC

Table No.	Population	IDSL No. / Example Shell	Title	Programming Notes	QC Level	Deliverable Priority
3.13	Tissue fluid Parameter	GSK1265744/LAI114433 Table 11.8	Listing of Individual Tissue and Fluid to Blood Plasma or Tissue vs Fluid Cabotegravir PK Parameter Ratios	Ratios of tissue fluid vs plasma or tissue vs fluid for AUC(0-t), AUC(0-∞), Cmax, AUC(0-Wk4), AUC(0-Wk8), AUC(0- Wk12), include flags for evaluable data and injection location variables	2	SAC

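### The time-matched AUC(0-last) ratios have no common end time, so the tissue or fluid:plasma ratio is biased whenever the two matrices stop being quantifiable at different times

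*SAP*

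**What the plan says.** Protocol 9.4.2 lists "Ratios of time-matched AUCs tissue matrices/luminal fluid: blood plasma where data permit" among the secondary PK parameters. SAP 8.3 item 10 repeats the aim and names the intervals: "Ratios of time-matched AUC(0-∞), AUC(0-last), AUC(0-Wk4), AUC(0-Wk8) and AUC(0-Wk12) tissue matrices/luminal fluid: blood plasma". The ratio of AUCs is a stated secondary endpoint in Protocol 3 and SAP 2.2.

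The rules that produce the numbers are these:

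- **SAP 8.3 item 4** runs the AUC "from time zero to the last quantifiable concentration (AUC(0-last"), and applies this to plasma, CT, CVF, RT and RF alike.
- **SAP 8.2** samples plasma at "Weeks 4, 8, 12, 24, 36, and 52 (CWk4, CWk8, CWk12, CWk24, CWk36 and CWk52"), after the first-week samples. For the rectal matrices it gives "Rectal tissue (RT) and rectal fluid (RF) in men and women (as data permit): Day 3 (C48h), Day 8 (Cd8), Weeks 4, 8, and 12". CT and CVF follow the same schedule as RT and RF.
- **The SAP 8 table**, in the row on parameters derived by the programmer, forms the ratios from stored parameters: "From SDTM PP file: VT:blood plasma, CT:blood plasma, CVF:blood plasma, CT:CVF, VT:CVF in women", followed by the rectal ratios and a list that includes AUC(0-last).
- **SAP 11.1.3**: the Table 3.8 note asks for "Ratios of Tissue or fluid vs plasma for AUC(0-t") and the Table 3.13 note for "Ratios of tissue fluid vs plasma or tissue vs fluid for AUC(0-t"). Table 3.10 does the same for tissue against fluid. AUC(0-t) stands where the other sections have AUC(0-last).

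None of these places defines time-matched for AUC(0-last) or contains a step that cuts the two AUCs at a shared time.

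**The concern.** A ratio of two AUCs measures penetration only if both cover the same interval. AUC(0-Wk4), AUC(0-Wk8) and AUC(0-Wk12) have common limits by definition. AUC(0-last) does not: its upper limit is set separately by each matrix's schedule and assay sensitivity.

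The documents give reasons to expect different end times. Protocol 2.2 puts the plasma half-life at about 21-50 days, and Protocol 4.6.1 expects residual drug for up to 52 weeks in some subjects. Table 1 in Protocol 2.1 shows non-quantifiable values in all three tissues in the earlier 400 mg study, so tissue may end before Week 12.

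What is at stake is a secondary descriptive ratio that does not match its label and can disagree, in the same Table 3.8, with the AUC(0-Wk12) ratio for the same subjects. The tissue:fluid AUC(0-last) ratios in Table 3.10 share the fault if one of the pair becomes non-quantifiable earlier.

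**Working it through.** The plan gives no figure for this ratio, so there is none to reproduce.

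**Step 1: direction, without a model.** Let tT and tP be the last quantifiable times in tissue (or fluid) and plasma, with AUCs A_T and A_P.

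- Ratio as the rules form it: A_T(0,tT) / A_P(0,tP).
- If tP > tT, dividing by the common-interval ratio A_T(0,tT)/A_P(0,tT) leaves A_P(0,tT)/A_P(0,tP), which is below 1.
- If tP < tT, the same step leaves A_T(0,tT)/A_T(0,tP), which is above 1.
- If tP = tT, the factor is 1.

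**Step 2: size, closed form.** Assume mono-exponential decline with half-life h and a constant tissue:plasma ratio. The factor is

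F = (1 − 2^(−tT/h)) / (1 − 2^(−tP/h)).

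Inputs: h = 21 and 50 days (Protocol 2.2), and ln 2 / (9.19×10⁻⁴ per hour) = 754 h = 31.4 days (updated absorption constant, Protocol 4.5).

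Example with h = 31.4, tissue to Week 12 (84 days), plasma to Week 24 (168 days): (1 − 0.1566)/(1 − 0.0245) = 0.8434/0.9755 = 0.865.

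| h (days) | Tissue Wk 12, plasma Wk 12 | Tissue Wk 12, plasma Wk 24 | Tissue Wk 12, plasma Wk 52 | Tissue Wk 8, plasma Wk 24 | Tissue Wk 8, plasma Wk 52 |
|---|---|---|---|---|---|
| 21 | 1.000 | 0.941 | 0.938 | 0.846 | 0.843 |
| 31.4 | 1.000 | 0.865 | 0.844 | 0.727 | 0.710 |
| 50 | 1.000 | 0.762 | 0.692 | 0.598 | 0.543 |

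Opposite case, with h = 21, tissue to Week 12, plasma to Week 8: (1 − 0.0625)/(1 − 0.1575) = 0.9375/0.8425 = 1.113.

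**Step 3: let the quantification limit set plasma's end time.** Neither document states a plasma limit (LLQ), and it decides the matter. With Cmax 1.35 µg/mL and h = 31.4 days, Week 24 plasma is roughly 1.35 × 0.0245 = 0.033 µg/mL. That is quantifiable at an LLQ of 0.025, and plasma then outlasts tissue. At an LLQ of 0.05 it is not, and both matrices end at Week 12.

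The SAP 8.3 linear-up/log-down trapezoid was run on the SAP 8.2 nominal times (plus time zero, with tissue set to zero there). Inputs:

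- biexponential profile with an assumed rise half-life of 24 h;
- h = 21, 31.4, 40 and 50 days;
- Cmax 1.35 or 3 µg/mL (the female and male predictions in Protocol 4.5);
- assumed plasma LLQ 0.01, 0.025, 0.05 and 0.1 µg/mL;
- constant true ratio.

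| Last quantifiable tissue sample | Ratio as the rules form it, fraction of truth | With a common end time |
|---|---|---|
| Week 12 | 0.68-0.99 | about 0.99 |
| Week 8 | 0.53-0.88 | about 0.99 |

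A rise half-life of 48 h barely moves the rule-based ranges (0.67-0.99 and 0.52-0.88). The remaining 1% after matching arises because tissue has fewer early samples than plasma. The 0.99 at the top of the Week 12 row is the case where the end times coincide and nothing is wrong.

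**The case against.** The strongest reply is that time-matched already tells the analyst to cut both AUCs at the same time. On that reading the programmer's row says only where the ratio is taken from, matched partial AUCs could be stored in that file, and the table notes are shorthand. It is fair that nothing in the SAP forbids matching. But no text defines or implements it, and the only stated definition of AUC(0-last) is matrix by matrix. An analyst who follows items 4 and 10, the SAP 8 table and the table notes gets the unmatched ratio. If truncation is intended, one sentence records it.

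A second reply is that the sizes rest on assumptions, and this stands:

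- No assay limit is given, and the treatment of values below it is left to standards not included with these documents.
- Week 52 is plasma's sampling limit, not its expected end. In the grid, plasma reaches it only at Cmax 3, 50 days and LLQ 0.01; without that case the Week 12 minimum is about 0.70.
- Protocol 4.5 attributes the higher male Cmax to faster absorption, so Cmax 3 with a 50-day half-life is an unlikely pairing.

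The ranges illustrate what can happen; they say nothing about how often.

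Third, the study is descriptive, with about 16 evaluable subjects and no hypothesis test, and three of the five AUC ratios have fixed limits. That limits the consequence, but it does not make a mislabelled ratio correct.

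**Conclusion.** The point holds. As written, the SAP's rules do not produce the time-matched AUC(0-last) ratio that SAP 8.3 item 10 and Protocol 9.4.2 ask for. The direction needs no model: low when plasma is quantifiable after the tissue or fluid's last quantifiable time, high when plasma ends first, nil when they end together. Under the stated assumptions, the ratio is 0.68-0.99 of truth with tissue to Week 12 and 0.53-0.88 with tissue to Week 8.

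Three stronger readings are tempting, and the documents do not support them:

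- **That the ratio will always, or usually, be low.** This depends on assay limits that are not stated.
- **That rectal ratios will be hit hardest, by a known amount**, because rectal tissue was often non-quantifiable in the earlier study. This study's tissue limit and imputation rules are not in the documents, so no size can be given.
- **That the trial's conclusions on penetration are compromised.** The primary endpoints are concentrations, and the AUC(0-Wk4), AUC(0-Wk8) and AUC(0-Wk12) ratios have common limits.

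This is one secondary descriptive ratio that should be corrected before it is produced.

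**What to change.** Add one sentence to SAP 8.3 item 10, and repeat it in the programmer's row of the SAP 8 table and in the notes to Tables 3.8, 3.10 and 3.13:

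*For every AUC(0-last) ratio (tissue or fluid:plasma and tissue:fluid), both AUCs are partial AUCs from 0 to the earlier of the subject's two last quantifiable times in the paired matrices.*

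Taking the earlier of the two times matters: cutting only plasma at the tissue end time would leave the plasma-ends-first case uncorrected. Naming tissue:fluid extends the rule to Table 3.10. The ratio stays in the plan, so the protocol endpoint is unchanged.

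The cost is one repeated sentence and a partial-AUC request for each matrix pair in the noncompartmental analysis. No new data are needed. Every nominal tissue and fluid time after the injection is also a nominal plasma time, so little interpolation should be required.
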